### 9.3.1.2. Comparator Cohort

The Phase 2 cohort study will include comparators with no recorded vaccination for the COMIRNATY 2023-2024 Formula. To improve comparability with the COMIRNATY 2023-2024 Formula vaccinated cohort, patients included in the comparator cohort will be required to have a code indicative of a healthcare encounter, including one of the following:

- Presence of a code for a vaccine other than the COMIRNATY 2023-2024 Formula;
- Presence of a code indicative of an outpatient healthcare encounter.

Codes relating to other vaccines or outpatient visits are provided in [Annex 2 \(Appendix II\)](#).

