#### 9.7.2. Cohort Study

##### 9.7.2.1. Propensity Score Modeling and Matching

The COMIRNATY 2023-2024 Formula-exposed and the unexposed comparator cohorts will be created as described in [Section 9.2.3](#). Each cohort member will be described with respect to baseline covariates as listed in [Section 9.3.3](#). These cohort members will be included in the propensity score modeling and matching.

This study will use a single PS model that encompasses risk factors for multiple outcomes, an approach demonstrated in other studies conducted to fulfill post-licensure regulatory commitments and requirements to the FDA and other regulatory agencies ([Seeger et al., 2023](#); [Ziyadeh et al., 2020](#)). While not all risk factors may be associated with all outcomes to the same degree, adjusting for covariates that are weakly or not at all associated with a given outcome is expected to result in negligible bias if residual confounding is small ([Brookhart et al., 2006](#); [Myers et al., 2011](#)). Incorporating a wide array of outcome predictors

(Section 9.3.3) into the PS is expected to minimize residual confounding, producing groups with similar patterns of both measured and unmeasured factors (Guertin et al., 2016).

The PS model will consist of a logistic regression model that incorporates the pre-specified demographic and comorbidity covariates, healthcare utilization, and calendar month of vaccination or cohort entry as independent variables, and an indicator for receipt of the COMIRNATY 2023-2024 Formula as the dependent variable. Two-way interactions of all variables with calendar month of vaccination or cohort entry, or empirically defined variables that are potential confounders, may also be considered for inclusion in the following model:

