$$\begin{aligned} & \text{logit}\{P(T_i = 1 \mid \mathbf{X}_i)\} \\ &= \beta_0 + \beta_1 \text{Sex (binary)}_i + \beta_2 \text{Age (categorical)}_i \\ &+ \beta_3 \text{Calendar month (categorical)}_i + \beta_4 \text{Geographic region (categorical)}_i \\ &+ \beta_5 \text{Asthma (binary)}_i + \beta_6 \text{Non-malignant blood disorders (binary)}_i \\ &+ \beta_7 \text{Chronic lung disease (binary)}_i + \beta_8 \text{Down syndrome (binary)}_i \\ &+ \beta_9 \text{Heart disease (binary)}_i \\ &+ \beta_{10} \text{History of SARS-CoV-2 infection (binary)}_i \\ &+ \beta_{11} \text{Immunocompromised status (binary)}_i \\ &+ \beta_{12} \text{Kidney disorders (binary)}_i + \beta_{13} \text{Liver disorders (binary)}_i \\ &+ \beta_{14} \text{Neurological or neurodevelopmental conditions (binary)}_i \\ &+ \beta_{15} \text{Malignant neoplasms (binary)}_i + \beta_{16} \text{Obesity (binary)}_i \\ &+ \beta_{17} \text{Type II diabetes (binary)}_i \\ &+ \beta_{18} \text{Number of hospitalizations in prior year (continuous)}_i \\ &+ \beta_{19} \text{Number of emergency room visits in prior year (continuous)}_i \\ &+ \beta_{20} \text{Number of outpatient encounters in prior year (continuous)}_i \\ &+ \beta_{21} \text{Seasonal influenza vaccination (binary)}_i \\ &+ \beta_{22} \text{RSV vaccination (binary)}_i + \beta_{23} \text{Systemic immunomodulators (binary)}_i \\ &+ \beta_{24} \text{Oral corticosteroids (binary)}_i + \beta_{25} \text{Antivirals (binary)}_i \\ &+ \beta_{26} \text{Antibiotics (binary)}_i + \beta_{27} \text{Identified empiric variables (binary)}_i, \end{aligned}$$

where  $T_i$  denotes exposure status for individual  $i$ , with  $T_i = 1$  indicating a recorded vaccination of the COMIRNATY 2023-2024 Formula and  $T_i = 0$  indicating no recorded vaccination of the COMIRNATY 2023-2024 Formula.

A greedy digit-based matching algorithm will be used, in which patients exposed to the COMIRNATY 2023-2024 Formula are matched without replacement to comparator patients at a given level of precision defined by the number of digits of the PS (Parsons, 2001), to a maximum of 8 decimal places. When no further matches are available at a given level of precision, the number of digits is sequentially reduced until a maximum allowable caliper of 0.1 is reached, thereby ensuring that the matched cohorts are comparable with respect to the underlying measured risk factors. Matching by propensity score will be conducted within

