strata defined by age group and calendar period. A matching ratio (e.g., up to 1:10) may be implemented.

PS matching will produce a single matched cohort (the master cohort) that will be used to conduct all primary, secondary, and sub-group analyses for the study outcomes. Balance between the PS-matched cohorts will be evaluated by overlaying graphs of the PS distributions in COMIRNATY-exposed and comparator cohorts before and after PS matching. Additionally, standardized differences between the PS-matched cohorts for each covariate in the model will also be assessed. Variables with an absolute standardized difference less than 0.1 will be considered balanced (Austin, 2009). If a variable has a standardized difference that is greater than 0.1, further PS model modifications (e.g., addition of interaction terms) or inclusion of the imbalanced covariates in an outcome model will be considered (Normand et al., 2001). If there are confounders identified that would only be appropriate to include for one outcome and not the others, a separate PS model for the specific outcome will be considered.

Outcome-specific exclusion criteria will be applied to the master cohort after PS matching but before the outcome specific analysis; the matched cohort that remains will be the analytic cohort for that specific outcome. The matched comparators of individuals excluded for outcome-specific exclusion criteria will also be excluded from the outcome-specific analysis.

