#### **9.7.2.3. Secondary Analysis**

The main analysis will compare the occurrence of safety outcomes in the COMIRNATY 2023-2024 Formula-exposed group to that of the matched comparator group. Secondary analyses will conduct this comparison separately, including recalculation of the matching ratio and accounting for individuals who are included in both study cohorts for various subsets of the matched comparator group, including:

- Comparators who, on cohort entry, received a 2023-2024 formulation of a COVID-19 vaccine other than COMIRNATY (i.e., Moderna or Novavax)
- Comparators who received a non-COVID-19 vaccine on cohort entry
- Comparators who did not receive a vaccine on cohort entry but had another type of outpatient health encounter.

090177e1a5be86fe\Approved\Approved On: 19-Mar-2026 15:57 (GMT)

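### The secondary comparisons split one pooled propensity-score match by comparator type, so covariate balance is not assured within the smaller vaccine-type comparator groups and is not checked there

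*Protocol*

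**What the plan says.** Protocol section 9.7.2.1 fixes the following.

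- **One model.** "This study will use a single PS model that encompasses risk factors for multiple outcomes". It has "an indicator for receipt of the COMIRNATY 2023-2024 Formula as the dependent variable", and the reference level is defined as "indicating no recorded vaccination of the COMIRNATY 2023-2024 Formula". The only stated exception to the single model is for a particular outcome, not a particular comparator.
- **A mixed reference group.** Under section 9.3.1.2 a comparator may qualify by "Presence of a code for a vaccine other than the COMIRNATY 2023-2024 Formula" or by an outpatient encounter.
- **One match.** Matching is within "strata defined by age group and calendar period". Comparator type is neither a matching factor nor a term in the model. "A matching ratio (e.g., up to 1:10) may be implemented".
- **One cohort for everything.** "PS matching will produce a single matched cohort (the master cohort) that will be used to conduct all primary, secondary, and sub-group analyses".
- **One balance check.** Standardized differences are assessed between the matched cohorts, with 0.1 as the limit. Section 9.7.2.2 adds that covariates found imbalanced in the matched cohorts enter the Poisson model.

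Section 9.7.2.3 repeats the comparison within each comparator type. The steps it names are "recalculation of the matching ratio and accounting for individuals who are included in both study cohorts for various subsets of the matched comparator group". It mentions no balance check, covariate adjustment or new score by type. By contrast, section 9.7.2.4 recognises that restriction can break matched sets and adds the PS as a covariate for the subgroup analyses.

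**The concern.** Matching on the probability of receiving COMIRNATY makes COMIRNATY recipients resemble the comparators taken together. People who received another COVID-19 vaccine, people who came for a different vaccine and people seen in clinic may still have different covariate profiles at the same score. Keeping one type then brings back an imbalance that the pooled match had averaged out.

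The comparisons with other vaccine recipients are of particular interest because everyone in them came for a vaccination. They would naturally be used to judge whether a primary result reflects the way comparators entered the cohort. They are also the comparisons in which balance is least secure, and the stated diagnostics would not show it.

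**Working it through.** The protocol gives no comparator shares, covariate effects or event counts, so there is no figure to reproduce. The argument is structural, and simulation under assumed inputs shows its possible size.

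**1. Structure.** Let e = P(T=1 | X), with T=1 for COMIRNATY. Matching on e gives f(X | T=1, e) = f(X | T=0, e). For comparator type c, f(X | c, e) is proportional to f(X | T=0, e) × P(c | X, T=0). It equals f(X | T=1, e) only if P(c | X, T=0) does not vary with X at fixed e. Nothing in the protocol secures that. Because the imbalance exists at a fixed pooled score, adding that score as a covariate, as in section 9.7.2.4, would not by itself remove it.

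**2. Cancellation.** With π_c the share of type c among matched comparators and d_c its standardized difference from COMIRNATY, the pooled difference is roughly Σ π_c d_c. This can be near zero while the individual d_c are not, and a type with a large share is held near zero.

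**3. Simulation A (assumed inputs).** n = 120,000, with two binary covariates (prevalence 0.30 and 0.25) and one standard normal.

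- Group log-odds coefficients: COMIRNATY 0.5, 0.2, 0.1; other COVID-19 vaccine 0.5, 0.6, −0.1; non-COVID-19 vaccine 0.1, −0.4, 0.3; outpatient visit 0. All were multiplied by 0.5, 1.0 or 1.5.
- Base mixes of COMIRNATY / other COVID-19 / non-COVID-19 / outpatient: 10/5/15/70, 10/20/20/50 and 10/2/5/83. This gives 3 × 3 = 9 scenarios.
- One pooled logistic PS, matched up to 1:10 on the score rounded to three decimals, then subset by type with ratio weights recalculated.
- Each binary covariate doubles the event rate, the continuous one multiplies it by e^0.4 per unit, and the true rate ratio is 1.

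| Comparators | Largest absolute SMD, 9 scenarios | Above 0.1 | Rate ratio when truth is 1 |
|---|---|---|---|
| Pooled | at most 0.006 | 0 of 9 | 0.999 to 1.004 |
| Other COVID-19 vaccine | 0.06 to 0.31 | 7 of 9 | 0.91 to 1.04 |
| Non-COVID-19 vaccine | 0.08 to 0.34 | 8 of 9 | 0.96 to 1.09 |
| Outpatient visit | 0.005 to 0.05 in eight, 0.10 in one | at the limit in one | 1.00 to 1.04 |

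**4. Cancellation in one scenario.** In the 10/5/15/70 mix at strength 1.0, comparator shares were 0.08, 0.16 and 0.76. For the continuous covariate the SMDs were +0.156 (other COVID-19) and −0.160 (non-COVID-19), with −0.001 pooled. Step 2 then predicts an outpatient SMD of (−0.001 − 0.08 × 0.156 + 0.16 × 0.160) / 0.76 = 0.0121 / 0.76 = 0.016. The simulation gave 0.017.

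**5. Simulation B (sensitivity to the assumed selection difference).** n = 400,000, with two standard normal covariates, COMIRNATY slopes 0.6 and 0.6, and comparators weighted to COMIRNATY within 200 score bins. SMDs in the other-COVID-19-vaccine subset, by that vaccine's slopes:

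| Slopes | SMDs |
|---|---|
| 0.6, 0.6 | 0.00, 0.00 |
| 0.6, 0.5 | −0.05, 0.05 |
| 0.7, 0.5 | −0.11, 0.10 |
| 0.9, 0 | about −0.47, +0.37 |

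In the last case the pooled SMDs were within 0.005, and those for the remaining comparators about 0.07 and −0.05.

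**6. After re-matching by type.** In the first two mixes of simulation A at strength 1.0, estimating the PS for COMIRNATY against each type and re-matching gave absolute SMDs of at most 0.014 and null rate ratios of 0.99 to 1.01.

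**The case against.** - **The outcome-model remedy may carry over.** Section 9.7.2.3 repeats the main comparison, and section 9.7.2.2 puts imbalanced covariates into the Poisson model. On a generous reading the secondary models inherit this. But its trigger is imbalance in the matched cohorts, and no check by type is stated that would set it off. What stands is that part of the repair already exists in the plan and needs to be extended.
- **The size depends on chosen inputs.** This stands. Recipients of the two COVID-19 vaccines may be selected almost alike, in which case the imbalance is nil.
- **The bias is modest and the analyses are secondary.** Null rate ratios of 0.91 to 1.09 are far from the signal rule in section 9.3.2 (rate ratio above 3.0 with P below 0.01). This stands as a limit on severity. These comparisons are still reported as estimates, and an imbalance above the protocol's own limit should not pass unseen.
- **A stronger reading.** A reader might infer that all three secondary comparisons are unbalanced, or in effect unadjusted. The documents do not support that. Age group and calendar period remain controlled because they define the matching strata. The pooled score still gives partial adjustment. A comparator type that makes up most of the pool stays near balance.
- **Deferral to a separate plan.** This is not available: section 7 describes the document as a combined protocol and SAP, and Annex 1 lists no standalone documents.

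**Conclusion.** The point holds as a gap in assurance. The method as fixed does not secure covariate balance between COMIRNATY and a single comparator type, chiefly the two vaccine types if they are the smaller part of the pool, and the stated check cannot reveal the failure. It does not follow that balance must fail.

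The largest subset SMD ran from about 0 to 0.47 across the assumed inputs. The null rate ratios of 0.91 to 1.09 come from simulation A alone. Both ranges rest on assumed comparator shares, selection effects and outcome effects, none of which the protocol gives. The primary pooled comparison is not affected. This should be corrected, but it does not threaten the study's main result.

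**What to change.** In sections 9.7.2.1 and 9.7.2.3, state that after subsetting, standardized differences will be computed and reported for COMIRNATY against each comparator type separately, with the same 0.1 limit.

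- **Minimum:** covariates above 0.1 in a given comparison enter that comparison's Poisson model, which extends the section 9.7.2.2 rule. For rare outcomes the model may support few such terms.
- **Preferred:** for each comparator type, re-estimate the PS (COMIRNATY against that type), re-match within age group and calendar period, and apply the 0.1 check. Keep the master cohort for the primary analysis.

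The minimum needs three more balance tables and possibly some added model terms. The preferred form needs three more runs of an existing program, and the matched COMIRNATY populations would then differ across the three comparisons and have to be described. Either form changes the protocol text, and section 10.3 notes that changes may need IRB re-review. Version 3.0 is dated 18 March 2026 and the final report is planned for 30 April 2026 (13 + 30 = 43 days later), so the minimum form may be the practical one.

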#### **9.7.2.2. Primary Analysis**

Once the matched cohorts have been created, the incidence rate of each safety outcome will be estimated among the COMIRNATY 2023-2024 Formula-exposed group and its matched comparator group. The rate ratio will be estimated using unconditional Poisson regression that accounts for both the matching ratio (i.e., a weight representing the number of COMIRNATY 2023-2024 recipients divided by the number of comparators in each individual strata) and individuals who are included in both study cohorts (i.e., using a REPEATED statement with an independent working correlation structure). If standardized differences show covariate imbalances in the matched cohorts, imbalanced covariates will be included in the unconditional Poisson models.

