### 9.3.2. Outcomes

In both the SCRI and cohort studies, the pre-specified safety outcomes of interest will include the following:

- ADEM
- Anaphylaxis
- Bell's palsy
- CVST
- Convulsions/seizures (non-febrile)
- Encephalomyelitis
- Glomerulonephritis
- Guillain-Barré syndrome
- Herpes zoster
- Immune-mediated myositis
- Immune thrombocytopenia
- Kawasaki disease
- Multi inflammatory syndrome (in children and adults)
- MS
- MI
- Myocarditis/pericarditis
- PE
- Stroke, hemorrhagic
- Stroke, ischemic
- Transverse myelitis

In addition, in Phase 2 of the study, the following pregnancy outcomes will be assessed in pregnant women or their infants, if sample size permits:

- Spontaneous abortion
- Stillbirth
- Preterm birth
- Major congenital malformations
- Small for gestational age

Code lists for the safety outcomes of interest are provided in [Annex 2 \(Appendix III\)](#). Corresponding site of care requirements are listed in Table 2. When possible, outcomes will be defined using a validated claims-based algorithm with high performance ([CBER, 2021](#)).

If a safety signal is detected in the interim report, then medical records will be retrieved for a subset of participants to confirm the presence of that study outcome. A safety signal that requires confirmation through medical record review will be defined as a rate ratio of > 3.0 and a corresponding P value of < 0.01 in the primary analysis of the SCRI design (details in [Section 9.7.1.1](#)). Additionally, medical record review may be conducted for analyses beyond the primary SCRI analysis if a safety signal (defined as a rate ratio of > 3.0 and a corresponding P value of < 0.01) is detected in the interim or final report. Medical records may also be retrieved for AESIs with estimates approaching the pre-specified safety signal threshold.

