## 9.7. Data Analysis

### 9.7.1. SCRI

#### 9.7.1.1. Primary Analysis

Descriptive statistics will be used to summarize the baseline characteristics of those who receive the COMIRNATY 2023-2024 Formula. Counts of each safety outcome of interest will be reported within pre-specified risk and control windows. Then, the observed incidence rates of the outcomes of interest will be estimated in the risk window and the control window. Among the individuals who experience an outcome of interest in either the risk window or the control window (but not both), an exact conditional Poisson regression model with the natural logarithm of the person-time as the offset will be used to calculate the relative incidence (rate ratio) and corresponding 95% confidence interval (CI) of the risk period relative to the control period. With the self-controlled design, whereby each individual serves as their own comparator, the analysis accounts for the factors that vary across but not within individuals (i.e., time-invariant covariates).

The results from the SCRI utilizing the Optum pre-adjudicated claims database will be presented in the interim report, while results from the SCRI utilizing the ORD will be presented in the final report.

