#### 9.7.2.4. Subgroup Analysis

If sample size permits, the main analysis will be restricted to the following subgroups:

- Individuals with concomitant administration of a non-COVID-19 vaccine (e.g., seasonal influenza, RSV) on cohort entry date; specific analyses will be performed among individuals receiving seasonal influenza vaccine and those receiving RSV vaccine
- Immunocompromised individuals
- Individuals with specific baseline comorbidities, such as a chronic lung, heart, kidney or liver condition; cancer; Down syndrome or other neurological or neurodevelopmental disorders; and blood disorders
- Individuals with prior SARS-CoV-2 infection
- Individuals with prior COVID-19 vaccination
- Pregnant women
- Individuals aged < 18 years
- Individuals aged  $\geq$  65 years

For the subgroup analysis, the propensity score will be included in the model as a covariate, given that some matched strata may be broken by restricting both the COMIRNATY 2023-2024 Formula cohort and the comparator cohort by the above attributes. As with the primary analysis, unconditional Poisson regression will be used, and the model will account for individuals who are included in both groups.

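### When one arm has no events, the Phase 2 Poisson model with robust variance gives falsely extreme P values and intervals, and the plan has no rule for that case

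*Protocol*

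**What the plan says.** For the cohort study, Protocol Section 9.7.2.2 states: "The rate ratio will be estimated using unconditional Poisson regression that accounts for both the matching ratio". The matching ratio enters as "a weight representing the number of COMIRNATY 2023-2024 recipients divided by the number of comparators in each individual strata". The same sentence requires the model to account for "individuals who are included in both study cohorts (i.e., using a REPEATED statement with an independent working correlation structure". In SAS this is a generalised estimating equation fit, whose usual inference is a Wald test on the empirical (sandwich) standard error.

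Section 9.7.2.3 repeats the comparison in three comparator subsets. Section 9.7.2.4 lists eight subgroup bullets and says: "As with the primary analysis, unconditional Poisson regression will be used", with the propensity score as a covariate. The matching ratio is left open in Section 9.7.2.1: "A matching ratio (e.g., up to 1:10) may be implemented".

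Section 9.3.2 extends the signal definition to the interim and final reports. The trigger is that "a safety signal (defined as a rate ratio of > 3.0 and a corresponding P value of < 0.01) is detected". The consequence outside the primary self-controlled analysis is discretionary: "medical record review may be conducted for analyses beyond the primary SCRI analysis". The section sets no minimum event count.

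The self-controlled (SCRI) analysis in Section 9.7.1.1 instead uses "an exact conditional Poisson regression model with the natural logarithm of the person-time as the offset". Nothing in Sections 9.7.2.2 to 9.7.2.4 says what is done when an arm has no events. Section 7 describes the document as protocol and SAP combined, and Annex 1 lists no standalone documents, so the plan points to no other place where this would be settled.

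**The concern.** Section 9.3.2 names 20 safety outcomes. Several are rare (ADEM, CVST, Kawasaki disease, transverse myelitis), and Section 9.7.2.4 cuts the cohort into groups such as people under 18 and pregnant women. Counting one primary, three secondary and eight subgroup contrasts gives 20 × 12 = 240 nominal fits, although the subgroup fits depend on adequate sample size. Some of these may have an empty arm.

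In that case the chosen variance estimator fails in a misleading way. It does not return a wide interval that warns the reader. It returns a huge or tiny rate ratio with a narrow interval and a very small P value. No event among recipients would read as strong protection, which in a safety study is false reassurance. One recipient event against none could meet both parts of the signal definition.

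**Working it through.** **Inputs.** The model, weights and variance come from Section 9.7.2.2, the signal rule from Section 9.3.2, and the ratio from Section 9.7.2.1 (1:10 as an example; 1:1 and 1:4 added as assumptions). The protocol states no sample size, event rate or power for Phase 2, so there is no figure of its own to reproduce. Assumed recipient numbers were 2,000 to 100,000. P values are taken as two-sided.

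**Why the standard error does not grow.** The robust variance of an arm's log rate is Σw²(y−μ)² / (Σwμ)².
- Arm with d events, rare outcome, constant weight: about w²d/(wd)² = 1/d.
- Arm with no events, equal person-time: Σ(wμ)²/(Σwμ)² = 1/n, however small μ has become.

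So SE(log RR) ≈ √(1/d + 1/n). With d = 1 and n = 20,000 this is 1.00, while the log rate ratio runs to plus or minus infinity. Where the iterations stop changes the reported ratio but not the conclusion: with SE = 1, any fitted ratio above exp(2.576) = 13.1 gives P < 0.01. Stopping the empty arm's log rate at −20 to −30 gave, for 1 against 0, ratios from 6.7e3 to 7.3e9 and P from 1e-18 to 1e-114.

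**Refit of the planned model** (statsmodels GEE, independence correlation, robust variance, 20,000 recipients):

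| Recipient vs comparator events | Ratio | Robust SE | Wald P | Exact P |
|---|---|---|---|---|
| 1 vs 0 | 1:1 | 1.000 | 2e-101 | 1.0 |
| 3 vs 0 | 1:1 | 0.577 | numerically 0 | 0.25 |
| 0 vs 3 | 1:1 | 0.577 | numerically 0 | 0.25 |
| 1 vs 0 | 1:10 | about 1 | 8e-99 | 0.09 |
| 0 vs 3 | 1:10 | about 0.58 | 2e-257 | 1.0 |
| 4 vs 1 | 1:1 | √(1/4+1) = 1.12 | 0.21 | 0.38 |

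Exact P is the conditional binomial test with allocation by person-time. For 3 vs 0 at 1:1 it is 2 × (1/2)³ = 0.25; for 1 vs 0 at 1:10 it is 1/11 = 0.09. Model-based Wald P values in the one-event cells, across the assumed sizes and ratios, were 0.91 to 1.00, which places the fault in the sandwich variance. A robust score test of 1 vs 0 or 0 vs 1 gave P = 0.32. Adding the propensity score as a covariate left the 1 vs 0 result essentially unchanged. The last row shows that a sparse cell with events in both arms behaves.

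**How often an arm would be empty under no effect**, with m expected recipient events:
- 1:1, recipient events only: e^(−m)(1−e^(−m)) = 23%, 12% and 4.7% at m = 1, 2 and 3. The comparator-only pattern is equally likely.
- 1:10, recipient events only: e^(−10m)(1−e^(−m)) = 3.5%, 0.3% and 0.003% at m = 0.1, 0.5 and 1.
- 1:10, comparator events only: e^(−m)(1−e^(−10m)) = 57%, 71%, 60% and 37% at m = 0.1, 0.2, 0.5 and 1.

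**The case against.** A reader might infer that Phase 2 will regularly turn single events into safety signals. The documents do not support that.
- The false-signal pattern depends on the ratio. At 1:10, the only ratio the protocol names, it has probability 3.5% or less at 0.1 or more expected recipient events. The common error there is false protection, which cannot meet RR > 3.0.
- Record review is mandatory only for a signal in the primary SCRI analysis, which already uses an exact model. Elsewhere it is optional, and a review would look at the very event behind the flag.
- The Wald test is an inference. The protocol does not say which P value feeds the rule, and a robust score test would not fire.
- SAS 9.4, the stated software, was not run. With the empty arm as reference level, some refits gave a missing or erratic standard error (about 4 to 57) instead of a tiny P value; others gave the same result under either coding.
- No event counts are given. With a source database of about 12.6 million people in 2021 and up to one year of follow-up, empty arms in the full-cohort comparison are not shown to be likely, and subgroups are run only if numbers allow.

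All of this stands as a limit on size and direction. It does not remove the defect: the sample-size condition has no threshold, covers only the subgroups and does not address events per arm, and a missing or erratic standard error is no valid result either.

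A second tempting reading is that all low-count Phase 2 cells need the SCRI's exact model, for example below five events. That also goes too far. The 4 vs 1 cell is not falsely significant, and the SCRI model conditions within a person across two windows, which is a different data structure from matched sets.

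**Conclusion.** The point holds in a narrow form and should be fixed. With an empty arm, the planned model and its usual robust Wald inference give a P value and interval that are wrong by many orders of magnitude, in either direction. The failure is confined to zero cells; common outcomes in the full cohort are unaffected.

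Frequency cannot be stated from the protocol. It is most plausible for the rarest outcomes within subgroups and comparator subsets. At high matching ratios the main risk is a spurious protective effect; near 1:1 both directions are equally likely under no effect. The conclusion assumes that the P value reported and used in Section 9.3.2 is the Wald P from the empirical standard error. If a score P value is intended, the plan should say so, since nothing in it does.

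**What to change.** Add a zero-event rule to Sections 9.7.2.2, 9.7.2.3 and 9.7.2.4:
- When either arm has no events, report no Wald P value or confidence interval for the rate ratio.
- Report events and person-time by arm, an exact conditional P value (binomial, allocation by person-time) or a robust-score P value, and a one-sided exact limit for the rate ratio.
- In Section 9.3.2, apply RR > 3.0 and P < 0.01 to that P value. With no comparator events the ratio is unbounded, so the P value decides.

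For orientation, with no comparator events the exact two-sided P falls below 0.01 at 8 recipient events at 1:1 (2/2⁸ = 0.008), 3 at 1:4 (1/5³ = 0.008) and 2 at 1:10 (1/11² = 0.008). The rule therefore still allows a flag on two events at 1:10.

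The cost is a few sentences and a small amount of programming. In these cells the exact result carries neither the propensity score covariate nor the correction for people in both cohorts and, if the ratio varies between sets, it does not carry the weights. That should be stated beside the result. Cells with events in both arms keep the planned model.
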